6.2. Research question and primary objectives

To confirm the safety of this drug when used in CHF patients with moderate renal impairment under actual medical practice.

[Reason for this objective]

Moderate renal impairment was contraindication in the indication of hypertension but not in the indication of CHF. In the domestic phase III study, use experience in Japanese CHF patients with moderate renal impairment was limited.

In the Drug Use Investigation in Japanese hypertension patients, 470 in total 3166 patients with moderate or severer renal impairment received, even though eplerenone was contraindicated in those patients. The incidence rate of treatment-related AEs observed in these 470 patients was higher than that in the other population. Hyperkalaemia was observed at the highest incidence rate in these patients. Treatment-related adverse events observed in more than 3 patients were hyperkalaemia in 8 patients (1.70%), renal impairment in 4 patients (0.85%) and blood potassium increased in 3 patients (0.64%).

For the risk mitigation, following sentences are added in the Dosage and Administration section (for CHF indication) in J-PI: Patients with moderate renal impairment should start with 25 mg every other day and the maximum dosage should be 25 mg once daily; dose should be reduced or interrupted according to serum potassium level and patient's conditions. In view of this situation, it is important to confirm safety on use in Japanese CHF patients with moderate renal impairment for risk management of this drug. Therefore, drug use investigation for Japanese CHF patients with moderate renal impairment will be conducted.

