7.3.8. Adverse events

Regardless of causal relationship with this drug, the following information related to all adverse events that occur between the start of administration and the last day of the observation period (the last day of observation if treatment is discontinued) should be entered in the section of adverse events. Conduct a detailed investigation separately if the sponsor judges it necessary.

- · Presence/absence of adverse event
- Name of adverse event
- Category of adverse event
 Also enter whether the entered adverse event is an "even
 - Also enter whether the entered adverse event is an "event related to hypotension" or an "event related to hyperkalaemia."
- Date of occurrence
- · Procedure ([1] Change of treatment with this drug; [2] Additional treatment for the adverse event)
- Seriousness
- Whether or not the event(s) has led to death; Whether or not the event(s) has led to hospitalization. If the event has led to death, enter information on whether or not it is "cardiovascular death," or if the event has led to hospitalization, enter information on whether or not it is "hospitalization due to a cardiovascular event."
- Outcome of the adverse event to present; Outcome date

Causal relationship with this drug

If there is any adverse event related to abnormal changes in test values from clinical laboratory tests and physiological function tests, etc., enter the following information in the section of tests related to adverse events.

- · Laboratory parameter
- · Site reference value
- Unit
- Test date
- Results

Cardiovascular deaths are defined as deaths due to any of the following causes:

- Cardiac failure
- Myocardial infarction
- Arrhythmia (Atrial fibrillation, Atrial flutter, Arrhythmia supraventricular, or Ventricular arrhythmia)
- Stroke or cerebrovascular attack
- Other causes related to cardiovascular system

If any adverse event corresponding to "renal impairment" is observed, enter information on drugs other than this drug and "7.3.4.1.1. Relevant drugs" (Refer to the section "7.3.4.2. Other previous treatment drugs and concomitant drugs [collect information for subjects who have any adverse event corresponding to "renal impairment"]).

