6. ENDPOINTS AND COVARIATES

6.1. Safety Endpoints

- Adverse reactions: An adverse reaction is an AE related to study drug as judged by the physician.
- Serious adverse reactions: A serious adverse reaction is an adverse reaction that is serious as judged by the physician.
- AEs
- Serious adverse events (SAEs): A SAE is an AE that is serious as judged by the physician.
- Major investigation items: Events included in each major investigation item are defined as follows:
 - Hyperkalaemia: This includes all AEs indicated as "Hyperkalaemia-related event" or "Combination of the above two events ("Hypotension-related event" and "Hyperkalaemia-related event")" in the CRF.

Hypotension-related events: These include all AEs indicated as "Hypotension-related event" or "Combination of the above two events ("Hypotension-related event" and "Hyperkalaemia-related event")" in the CRF.

- Other investigation items
 - Renal impairment-related events

Renal impairment-related events are events coded as one of the following preferred terms (PTs):

Acute kidney injury, Chronic kidney disease, Renal failure, or Renal impairment.

- Blood pressure (systolic, diastolic)
- Body weight
- Laboratory tests (serum creatinine, serum potassium, BUN)

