7. HANDLING OF MISSING DATA

If the severity, treatment, or outcome of an AE is missing, it will be regarded as having a value of "unknown" at the time of a statistical summarization.

If an observation for the dosing status, a safety endpoint, an effectiveness endpoint, or a laboratory test was done outside its time window (Appendices A1.1, A1.2, and A1.3), the obtained data will be regarded as missing data and will not be imputed.

Cleaning-uncompleted data will be basically handled as follows. Detailed handling of individual items will be explained in separate lists.

• Items for which data are missing: For both summarization and listing, their values will be handled as missing data (or "unknown" in the case of a categorical variable).

- Items for which data are inconsistent: For both summarization and listing, their values will be handled as missing data.
- Items for which signature is missing: For both summarization and listing, any data in a CRF with no signature of the contract physician (including when the CRF is signed only by individuals other than the contract physician) will be handled as missing data.

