8.2.3. Safety Analysis

8.2.3.1. Adverse Reactions

• All Adverse Reactions

Adverse reactions will be summarized by system organ class (SOC) and preferred term (PT) in terms of number and proportion of patients.

• Serious Adverse Reactions

Serious adverse reactions will be summarized by SOC and PT in terms of number and proportion of patients.

• Details of Adverse Reactions

Adverse reactions will be summarized by each of the categorizations below for each PT in terms of number and proportion of patients:

- Seriousness [serious, non-serious]
- Known/unknown [known, unknown]
- Action taken [permanent discontinuation, temporary discontinuation or dose reduction, others (none, dose increase)]
- Outcome [not recovered, recovered with sequelae, improved, resolved/recovered, unknown, death]

If the same patient experienced the same adverse reaction (of the same PT) more than once, the patient will be counted as follows:

- Seriousness: If the events include both serious and non-serious ones, the patient is counted as a
 patient experiencing a serious reaction.
- Known/unknown: If the events include both known and unknown ones, the patient is counted as
 a patient experiencing an unknown reaction.
- Time to onset (days): The first onset will be counted.
- Action taken: If multiple actions were taken, a single action will be chosen according to the
 order of priority of (1) permanent discontinuation, (2) temporary
 discontinuation/dose reduction, and (3) others (none, dose increase).
- Outcome: The outcome of the last event will be used.

• Major Investigation Items

The major investigation items listed below will be summarized in terms of number and proportion of patients:

- Hyperkalaemia
- Hypotension-related events

In addition, each major investigation item will be summarized by action taken and by outcome for each PT in terms of number and proportion of patients.

• Other Investigation Items

Renal impairment-related events will be summarized in terms of number and proportion of patients. In addition, the events will be summarized by action taken and by outcome for each PT in terms of number and proportion of patients.

• Onset Time of Adverse Reaction

All adverse reactions, hyperkalaemia, hypotension-related events, and renal impairment-related events will be summarized by time of first onset [Appendix A1.1] for each SOC and PT in terms of number of patients.

Relationship Between Concomitant Drugs and Adverse Reactions

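### Hyperkalaemia and hypotension are counted only when the site assigns the CRF category, so a plainly coded event without that indication falls outside the pooled item

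*SAP*

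**What the plan says.** SAP 6.1 sets out two major investigation items. For hyperkalaemia: "This includes all AEs indicated as 'Hyperkalaemia-related event", or the option combining both categories. For hypotension: "These include all AEs indicated as 'Hypotension-related event", or the same combined option. Neither definition adds a preferred term, a term grouping, or a potassium or blood-pressure threshold.

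The third group in that section is built differently: "Renal impairment-related events are events coded as one of the following preferred terms (PTs", followed by four named terms.

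The indication comes from the site. Protocol 7.3.8 instructs the investigator: "Also enter whether the entered adverse event is an 'event related to hypotension' or an 'event related to hyperkalaemia". It gives no criterion for what counts as related.

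SAP 8.2.3.1 then uses these definitions: "The major investigation items listed below will be summarized in terms of number and proportion of patients". It breaks each item down by action taken and outcome for each preferred term, and it uses the items again in the onset-time and concomitant-drug tables. Neither document states a rule for reconciling the indication with the coded term.

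**The concern.** Hyperkalaemia is the first important identified risk in Protocol 6.1 and a major investigation item in Protocol 7.3.10.1. The flag-based item is the only place where the SAP yields one pooled hyperkalaemia count. Its membership rests on how each of about 150 sites reads the category field.

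Potassium events can be expected to arrive under more than one term. Protocol 7.3.5 asks for clinically problematic laboratory changes to be entered as adverse events. Protocol 9.4.1 makes a test result that leads to a dosing change reportable, and Protocol Table 1 ties dosing to serum potassium. The earlier hypertension survey in Protocol 6.2 shows the two terms side by side among its 470 patients with moderate or severer renal impairment: "hyperkalaemia in 8 patients (1.70%), renal impairment in 4 patients (0.85%) and blood potassium increased in 3 patients (0.64%)". Whether a site classes a laboratory-term event as hyperkalaemia-related is left to that site.

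A disagreement would be awkward to interpret. The item count and the preferred-term table in the same report could differ with no explanation. No laboratory summary would help: serum potassium is a safety endpoint in SAP 6.1, but SAP 8.2.3.3 summarises blood pressure only, and SAP 9 provides potassium as a listing.

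**Working it through.** **1. Where an unindicated event goes.** Take an adverse reaction coded Blood potassium increased, with the hyperkalaemia category not assigned.

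| Output | Included? |
|---|---|
| Item incidence, action and outcome (SAP 8.2.3.1) | No |
| Onset time for the hyperkalaemia item (SAP 8.2.3.1) | No |
| Concomitant-drug table for hyperkalaemia (SAP 8.2.3.1) | No |
| Listing of events of each major item (SAP 9) | No |
| All adverse reactions by class and term, and their onset time (SAP 8.2.3.1) | Yes |
| All adverse events by class and term (SAP 8.2.3.2) | Yes |
| Subgroup tables by class and term, including eCLCr 30 to <50 mL/min (SAP 8.2.3.4) | Yes |
| General adverse event and reaction listings (SAP 9) | Yes |

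The tables that keep the event show Hyperkalaemia and Blood potassium increased on separate rows. Adding those rows can count a patient twice, so they do not give a pooled patient-level rate.

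**2. The plan's own figures.** From Protocol 7.5.2, for all CHF patients:

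- Rate: (3 + 56)/(111 + 1360) = 59/1471 = 4.01%, stated as 4.0%.
- Expected reactions in 1000 patients: 1000 × 0.040 = 40.0.
- Estimated-rate range: 0.040 ± 1.96 × √(0.040 × 0.960/1000) = 2.79% to 5.21%, stated as 2.8%-5.2%.
- Count range from exact binomial quantiles: 28 to 53, as stated.

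All reproduce.

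**3. Illustration of an under-count.** The documents give no rate of unindicated events, so the share m is an assumption. Expected count = 40.0 × (1 − m).

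| Share not indicated (assumed) | Expected count | Expected rate | Chance of a count below 28 |
|---|---|---|---|
| 0% | 40.0 | 4.0% | 1.8% |
| 5% | 38.0 | 3.8% | 3.6% |
| 10% | 36.0 | 3.6% | 7.0% |
| 20% | 32.0 | 3.2% | 21.2% |
| 30% | 28.0 | 2.8% | 47.4% |

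Each 10% removes about 4 reactions. Even at 20%, the count would stay at or above the planned lower limit about 79% of the time (100 − 21.2), so the shortfall would not usually be noticed.

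**4. What the survey adds.** Of the potassium reports in Protocol 6.2, 3/(8 + 3) = 27% carried the laboratory term, assuming distinct patients. If every such event went unindicated, an extreme case, 40.0 × (1 − 3/11) = 29.1 reactions would remain (2.9%). Eleven reports from another indication show that both terms occur. They do not show how sites would classify them.

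**5. The opposite error.** A site can also assign the category to an event that is not hyperkalaemia, such as worsening renal function. That raises the count, so the net direction cannot be derived from the documents.

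**The case against.** The strongest reply is that the primary objective is largely untouched. A reader might infer that the 8.4% (22/261) benchmark for moderate renal impairment would be understated. The SAP does not support that: 8.2.3.1 does not split the flag-based items by renal function, and 8.2.3.4 presents reactions by class and term in the eCLCr subgroups whether indicated or not. This stands, and it is why the illustration uses all CHF patients.

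A reader might also infer that SAP section 7 discards events whose category is blank. Its rule reads "Items for which data are missing: For both summarization and listing, their values will be handled as missing data" (or unknown for a categorical variable), but it governs only data left uncleaned, and it refers to separate handling lists that are not in the documents. Sponsor queries exist (Protocol 7.6.3.2), and the CRF itself is not available. Whether a blank is queried, or checked against the coded term, is therefore unknown.

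A third tempting inference is that the error must run towards too few events. Nothing in the documents shows that laboratory-term events are classified less often, and over-classification is possible too.

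Physician classification is also a legitimate method, used in SAP 6.1 for causality and seriousness, and it can capture unusual terms that a fixed list would miss. That supports keeping the indication, but not relying on it alone. Finally, the definition behind the clinical-study benchmark cannot be seen, so it cannot be judged whether the indication, the terms or their union matches it best.

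**Conclusion.** The point holds as a gap in definition with a cheap remedy. Read literally, SAP 6.1 leaves a plainly coded potassium or hypotension event out of its item when the category was not assigned, and neither document states a cross-check. The effect is confined to the item-level tables and listings; the events remain visible elsewhere by term.

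The size is unknown. The figure of about 4 fewer reactions per 10% not indicated (4.0% to 3.6% in 1000 patients) rests on the protocol's assumed 4.0% rate, an assumed share of unindicated events, and no offsetting over-classification. It shows sensitivity and is not an estimate of bias.

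**What to change.** In SAP 6.1, define each item as indicated in the CRF **or** coded to a short fixed list of preferred terms:

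- Hyperkalaemia: Hyperkalaemia, Blood potassium increased.
- Hypotension-related: for example Hypotension, Orthostatic hypotension, Blood pressure decreased.

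Beneath each item, show the indicated-only and term-only counts. Add a listing of discordant events and query them if the database is still open. SAP version 7.0 records observation as completed, so if tables already exist, label the new row as added after data collection.

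The cost is SAP wording, about one extra row per table and one listing; the indication and the coded term are both already collected. There are two downsides. The reported incidence may rise slightly, and wrongly indicated events stay in the union, which is why the component counts must be shown.

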7.3.5. Tests/clinical laboratory tests

Enter whether or not tests are implemented and test results for the clinical course from before administration of this drug to the last day of the observation period. Before administration of this drug, enter the latest test results for tests implemented during the period from three months before the start of administration to immediately before the start of administration (including the start date of administration) (For cardiac function tests: from six months before the start of administration). At the end of the observation period, enter the test results within one month after the last day of the observation period. If there are no test results for appropriate dates, enter the test results for the day of tests closest to the last day of the observation period. For any test results, enter the implementation date and test results. Regarding clinically-problematic abnormal changes in test values compared to the values before the start of administration, enter the details in the section of adverse events as well.

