Note: Adverse events are any and all unfavorable events (including clinically significant abnormal changes in laboratory tests) occurring in patients after starting treatment with this drug regardless of their causal relationship. Serious adverse events are any unfavorable medical occurrences that result in death, are life-threatening, require (or prolong) hospitalization, cause persistent or significant disability/incapacity, result in congenital anomalies or birth defects, or are other conditions which represent significant health hazards.

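### The four-term renal definition leaves renal reactions coded as laboratory changes out of the grouped renal summaries

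*SAP*

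**What the plan says.** SAP 6.1 (Safety Endpoints, other investigation items) defines the renal group by coded preferred term (PT): "Acute kidney injury, Chronic kidney disease, Renal failure, or Renal impairment". The list is closed. It contains no laboratory term, and no supplementary definition or physician flag is given.

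SAP 8.2.3.1 builds the renal results on this list: "Renal impairment-related events will be summarized in terms of number and proportion of patients". The same group is used for action taken and outcome, for time of first onset, and for the relationship with concomitant drugs.

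The two major investigation items are defined differently. For hyperkalaemia SAP 6.1 says "This includes all AEs indicated as" such on the CRF, so the investigator's category decides and the coded term does not. Hypotension-related events work the same way.

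Protocol 7.3.5 says of clinically problematic test changes: "enter the details in the section of adverse events as well". Protocol 7.3.5.3 includes serum creatinine and BUN among the tests. Protocol 7.7 plans to study the risk factors and onset time of reactions related to renal impairment and sets no limit by PT.

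**The concern.** The protocol's concept of a renal reaction is wider than the SAP's list. An investigator who sees a clinically important creatinine rise may report renal impairment or may report the creatinine rise itself. Only the first reaches the renal group, so the grouped count depends partly on how the event was worded.

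This matters because renal impairment is an important potential risk (Protocol 6.1), the primary objective concerns patients whose kidneys are already impaired (Protocol 6.2), and renal reactions are one of the two events used to justify the sample size (Protocol 7.5.2). No other renal-specific summary would catch the missing reactions. There is no CRF category for renal events. SAP 6.1 names serum creatinine and BUN as safety endpoints, but SAP 8.2.3.3 summarises blood pressure only and SAP 9 provides laboratory data as a listing.

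**Working it through.** **1. The plan's own figures (Protocol 7.5.2, Table 5).**

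- Moderate renal impairment: events (0 + 1) + (1 + 6) = 8; patients 37 + 224 = 261; 8/261 = 3.07%, given as 3.1%.
- Expected cases: 300 × 0.031 = 9.3 and 350 × 0.031 = 10.85, given as 9.3–10.9.
- 95% range in 300 patients: 0.031 ± 1.96 × √(0.031 × 0.969/300) = 1.14% to 5.06%, given as 1.1%–5.1%.
- All CHF patients: (1 + 1) + (4 + 12) = 18; 111 + 1360 = 1471; 18/1471 = 1.22%, given as 1.2%; 1000 × 0.012 = 12.0; 95% range 0.53% to 1.87%, given as 0.5%–1.9%.

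All reproduce. The sample-size arithmetic is not in question.

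**2. Where a related reaction coded to a laboratory PT goes.**

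| Output | Counted? |
|---|---|
| Grouped renal number and proportion (SAP 8.2.3.1) | No |
| Renal action taken and outcome (8.2.3.1) | No |
| Renal onset time (8.2.3.1) | No |
| Renal events by concomitant drug (8.2.3.1) | No |
| All adverse reactions by SOC and PT (8.2.3.1) | Yes, under its own PT |
| eCLCr subgroup table by SOC and PT (8.2.3.4) | Yes, under its own PT |
| Adverse reaction listings, including eCLCr 30 to <50 mL/min (9) | Yes |
| Listing of adverse reactions of renal impairment (9) | No, if it follows the 6.1 definition |

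The eCLCr subgroup table has no grouped renal row under either definition. It gives patients with any adverse reaction, then SOC and PT. PT rows cannot simply be added up, because one patient may appear in several.

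**3. Direction.** Every patient counted under the four terms is also counted under a longer list that contains them, so the longer list cannot give a smaller number of patients.

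**4. Size, as an assumed range.** Let *f* be the share of patients with a renal reaction whose only renal terms are laboratory terms. The four-term rate is then *p*(1 − *f*), where *p* is the rate with laboratory terms included. The documents give no *f* for renal reactions.

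| *f* (assumed) | *p* = 3.1%: rate | Cases in 300 | *p* = 1.2%: rate | Cases in 1000 |
|---|---|---|---|---|
| 0 | 3.1% | 9.3 | 1.2% | 12.0 |
| 10% | 2.8% | 8.4 | 1.1% | 10.8 |
| 25% | 2.3% | 7.0 | 0.9% | 9.0 |
| 50% | 1.6% | 4.7 | 0.6% | 6.0 |

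For example, at *f* = 10%: 3.1% × 0.90 = 2.79% and 300 × 0.0279 = 8.37.

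The grouped row the SAP now plans covers the whole Safety Analysis Set, so the 1.2% columns match it. The 3.1% columns describe a row that the SAP does not yet produce.

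**The case against.** The strongest reply is that nothing is hidden. The reactions appear by PT in the overall table and in the eCLCr subgroup table, which is where the primary objective is addressed. This stands. What is missing is the combined patient count and the grouped onset, action/outcome and concomitant-drug results.

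A second reply is that a diagnostic definition suits the concept. Protocol 7.3.1, on baseline classification, says renal impairment does not mean a transient laboratory abnormality. Protocol 7.3.8 also gives a separate place for the test values behind an event, so an investigator may well name the diagnosis. This is fair, and it is why the four-term result should stay as the main one. But a laboratory change becomes an adverse event only after a clinical filter (Protocol 7.3.5 and 9.4.1), and an adverse reaction also needs the physician's judgement that it is related. Such events are not incidental values.

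Third, the contrast with hyperkalaemia follows the protocol's tiers: identified risks have a CRF category and the potential risk does not. That explains the difference but does not fill the gap.

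Three stronger readings are tempting, and the documents do not support them:

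- *About a quarter of renal reactions are lost.* In the earlier hypertension survey (Protocol 6.2), potassium reactions split into 8 coded as hyperkalaemia and 3 as raised blood potassium. Taking 3/11 = 27% would turn 3.1% into 2.3% and 9.3 cases into 6.8. That share comes from a different kind of event, assumes no patient had both terms, and has an exact 95% interval of about 6% to 61%. The same source reports renal impairment in 4 of 470 patients and lists no renal laboratory term among the most frequent reactions. It shows only that both kinds of coding occur with this drug.
- *The study will look safer than its 3.1% benchmark.* The 8 planning cases are the sum of two Table 5 rows whose labels are not readable in the text available here. If both are diagnoses, the planning and analysis definitions may agree.
- *The sample size is wrong.* It is unaffected.

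**Conclusion.** The point holds as a limited one. The SAP's renal group is narrower than the reactions the protocol sets out to study, and any resulting error in the grouped renal count is downward. Its size cannot be derived from the documents. Under an assumed laboratory-only share of 10–50%, 3.1% would read as 2.8–1.6%, and 1.2% as about 1.1–0.6%. Zero is also possible. Even at 50% the reduced rates stay inside the protocol's stated sampling ranges (1.1%–5.1% and 0.5%–1.9%), so the shortfall would not stand out from chance variation in the results.

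SAP 4 treats all tests as exploratory and sets no decision rule, so no formal conclusion turns on this. It is a cheap improvement to how an important potential risk is reported. It does not invalidate the analysis.

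**What to change.** - Keep the four-term definition as the main result.
- Add a second, broader definition to SAP 6.1: the four terms plus laboratory PTs for reduced renal function, such as raised blood creatinine, raised blood urea, reduced GFR and reduced creatinine clearance. Check the exact names against the coding dictionary version in use. The current SAP postdates the end of observation, so draw the list from the dictionary and not from terms already seen in the data, and date it.
- Report both definitions side by side in the SAP 8.2.3.1 renal incidence, action/outcome, onset-time and concomitant-drug summaries, counting each patient once per definition.
- Add a grouped renal row, narrow and broad, to the eCLCr table in SAP 8.2.3.4, so that the result in moderate renal impairment can be set against the planning rate. State which PTs made up the 3.1%, so that the comparison uses the matching row.

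The cost is a longer term list and a few extra rows, with no new data. The broad count will be less specific and slightly less favourable.
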